Data will be summarized by group and in total. In summary tables of continuous variables, the minimum, maximum, mean, and standard deviation will be presented with one decimal place. We will use counts and percentages in table for categorical variables. The denominator for each percentage will be the number of participants within the group unless otherwise specified. All hypothesis testing will be carried out at a two-tailed Type I error rate of $\alpha = .05$ unless otherwise specified. P-values will be rounded to three decimal places with a minimum of < 0.001 in tables. If statistical methods change during analysis, this will be documented in all reports with justification. Additional analyses of these data will be inevitable, but any exploratory analyses will be clearly marked as such.

Statistical power analysis and sample size selection

IRT and DIF analyses require large samples due to the large number of free parameters to be estimated. The proposed sample size herein is larger than other successful implementations of these same analyses carried out in other IRT studies.¹⁶⁻¹⁹ Moreover, we have carried out computer simulations to determine if our proposed sample sizes will be sufficient to create IRT models. We assumed a one-factor model across two groups at $n = 100$ each with standardized factor loadings set to .7 for eight questionnaire items. We used two groups for this simulation to ensure that any pairwise model comparisons would have adequate power. For this simulation, we specified that a non-significant model χ^2 was a good fit, which is a conservative decision because this particular test is highly sensitive relative to other measures of model fit, especially with large samples. Across 500 iterations, a good-fitting model was identified across groups 90% of the time. Even dropping the sample size to as low as $n = 50$ would identify a good-fitting model 84% of the time.

Missing data

We will describe the rate of missing data on an item-by-item basis using frequency tables in R. We do not anticipate high rates of missing data, but we will conduct subgroup analyses by health literacy, site, and administration mode as need to help diagnose any problems with missing data. For DIF analyses, IRT models

Table 1	
Visit 1 (Baseline)	Description of instrument
Language Assessment	To determine testing in English or Spanish
Single Item Health Literacy Screener	To screen for possible literacy status

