Multiple regression analyses will be conducted using the *lm()* function in base R to test a moderation model for the PHQ-9 and PROMIS depression scale separately with health literacy (a continuous score from Health LiTT) acting as the proposed moderator between depression symptoms and pain intensity and interference, sleep disturbance, fatigue, and rumination. PROMIS profile scale scores will be entered into the regression model together. Health literacy will then be added as a moderator. In accord with our hypotheses, the addition of health literacy into the model should explain a significantly greater portion of the variance than symptom scores alone. PROMIS profile scale scores will then be removed from the model in a step-down procedure to determine the contribution of each scale to the model. We hypothesize that there will be a significant interaction between health literacy and symptoms scores. Specifically, we hypothesize that having higher health literacy will result in a stronger association between rumination and depression, whereas individuals with lower health literacy will evidence a stronger association between somatic symptoms (pain, fatigue, and sleep disturbance) and depression. Additionally, we predict that there will be a greater effect of health literacy for analyses involving the PHQ-9 than the PROMIS. We will also compare standardized beta coefficients to determine the strength of the effect for each variable. As we anticipate few instances of missing data due to our computerized administration, listwise deletion will be used in the presence of missing data.

Meaning and Purpose Analyses

DIF Analysis. In addition to the lordif approach described above, we will conduct DIF analysis using the moderated nonlinear factor analysis (MNLFA) approach, which allows health literacy to be continuous, rather than categorical (high versus low). Our analyses will examine the impact of health literacy on DIF as well as possible moderation by administration type (pencil-and-paper versus talking touchscreen). The MNLFA enables the examination of both variables simultaneously. Our a priori hypothesis is that DIF will be observed across levels of health literacy for paper-and-pencil based testing. We further hypothesize that DIF will also be found for the talking touchscreen, but for fewer items. Mplus permits IRT analyses with constraints imposed such that each item slope is linearly related to external variables – in our case, this would be:

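### The SAP predicts a larger health-literacy effect for the PHQ-9 than for PROMIS depression but gives no effect measure, test or interval for that difference

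*SAP*

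**What the plan says.** The SAP section on prediction of depression, with health literacy as a moderator, uses multiple regression with lm() "to test a moderation model for the PHQ-9 and PROMIS depression scale separately with health literacy" (the continuous Health LiTT score) as the moderator. The symptoms are pain intensity, pain interference, sleep disturbance, fatigue and rumination.

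The section states these expectations and comparisons:

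- On added variance: "the addition of health literacy into the model should explain a significantly greater portion of the variance than symptom scores alone".
- On moderation: "We hypothesize that there will be a significant interaction between health literacy and symptoms scores". Higher literacy is expected to strengthen the link between rumination and depression. Lower literacy is expected to strengthen the links between the somatic symptoms and depression.
- Between outcomes: "we predict that there will be a greater effect of health literacy for analyses involving the PHQ-9 than the PROMIS".
- Immediately afterwards: "We will also compare standardized beta coefficients to determine the strength of the effect for each variable".

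Missing data are handled by listwise deletion. No sample size is given for this analysis. The Overview under Statistical methodology sets the general default: "All hypothesis testing will be carried out at a two-tailed Type I error rate of" .05 unless otherwise specified.

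**The concern.** The between-outcome prediction needs an estimate of a difference and its uncertainty, and the plan produces neither. Added variance, the interaction terms and the step-down removal of scales are all judged within one outcome. What remains is to look at two sets of output and see which number is larger, or which is significant. Neither shows that the effects differ.

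The term effect is also left open. It could mean the variance added by health literacy, a particular interaction, or the interactions as a group. With five moderated symptoms, the answer can depend on which is chosen once results are visible.

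At stake is a substantive statement that one widely used depression scale is more sensitive to literacy than another. Following the plan exactly, that statement could be reported as confirmed with no evidence of a difference.

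**Working it through.** The documents give no power, error rate or sample size for this prediction, so there is no planned figure to reproduce. The check asks how often the prediction would be called right if the true standardized effects were equal.

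**Inputs.** Two-sided alpha .05, so the critical value is 1.96 (SAP, Overview). N of 300 to 728 is assumed: 728 is the number with a health literacy assessment (SAP, Study Objectives), and some of them lack later questionnaires. The correlation r between the two models' interaction estimates is assumed to be .5 to .8. The common noncentrality d is 0, 1, 1.96 (about 50% power) or 2.8 (about 80% power), also assumed.

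**Set-up.** Let z1 (PHQ-9) and z2 (PROMIS) be bivariate normal with mean d, variance 1 and correlation r.

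**Rule 1, larger estimate.** The two are exchangeable, so P(|z1| > |z2|) = 1/2. Simulated regressions with five symptoms, Health LiTT and five interactions (4,000 data sets per setting, residual correlation .6, N = 300, 566 and 728) gave 49% to 50% for added R-squared and 50% to 52% for a single interaction.

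**Rule 2, PHQ-9 significant and PROMIS not.** At d = 1.96, P(both significant) = 1/4 + arcsin(r)/(2π), ignoring the far tail. The rule's rate is 1/2 minus that.
- r = .5: 1/2 − (1/4 + 1/12) = .167
- r = .7: .500 − .373 = .127
- r = .8: .500 − .398 = .102

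Simulation (2,000,000 draws) gave .167, .126 and .103. With no effect (d = 0) it gave .041, .033 and .028. The range over all settings is 2.8% to 16.7%.

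**Rule 3, PHQ-9 significant and larger.** At d = 1.96 the rate is ½ × [1 − P(neither significant)]. At r = .5 this is ½ × (1 − 1/3) = .333. Simulation gave 30% to 33% at d = 1.96, 44% to 46% at d = 2.8, and 4% to 5% at d = 0.

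**Rule 4, counting over five interactions.** If the five comparisons were independent coin tosses, larger in at least one would have probability 1 − .5⁵ = .969, and larger in all five .5⁵ = .031. Simulation gave 96% to 98% for at least one, 50% to 51% for a majority, and 2% to 4% for all five.

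**A test of the difference.** T = (z1 − z2)/√(2 − 2r) has mean 0 and variance 1 when the effects are equal. So P(T > 1.96) = 2.5% and P(|T| > 1.96) = 5%. Simulation gave .025 and .050 for every r and d tried.

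| Rule, true effects equal | Called right |
|---|---|
| Larger standardized estimate | about 50% |
| PHQ-9 significant, PROMIS not | 3% to 17% |
| PHQ-9 significant and larger | 4% to 46% |
| Larger in at least one of five | 96% to 98% |
| Larger in all five | 2% to 4% |
| Two-sided 5% test of the difference | 2.5% |

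**Why the printed output is not enough.** With equal standard errors s, the standard error of the difference is s√(2 − 2r): 1.00s at r = .5 and 0.63s at r = .8. Two separate lm() fits do not report r. Treating them as independent gives √2 × s = 1.41s, which is 1.4 to 2.2 times too wide over that range.

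**The case against.** The strongest reply is that the plan does provide a comparison, namely of standardized betas. This disposes of one tempting criticism. A reader might infer that raw coefficients on a 0–27 score and a T score are to be set against each other; with standardization planned, the documents do not support that. But the sentence says the comparison is for each variable, which more naturally means ranking predictors within a model. Even read across outcomes, it carries no standard error, interval or rule.

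A reader might also infer that the prediction comes out right half the time whatever happens. The documents do not support that either, because they state no decision rule. The 50% holds only for the larger-estimate rule with equal true standardized effects. Unequal reliability (assumed .80 against .95) moves the added-R-squared rule to between 41% and 62%.

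Nor should every study in which exactly one interaction is significant be counted. At N = 728, with assumed standardized interactions of .05 to .08 and residual correlations of .5 to .7, that happens in 20% to 32% of studies. Only the half favouring the PHQ-9, about 10% to 16%, would support the prediction.

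Finally, this is one additional prediction in an observational moderation analysis, and the DIF analyses do not depend on it. That limits the weight of the point but does not supply the missing test.

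**Conclusion.** The point holds as a gap in the analysis method. The SAP makes a directional claim about a difference between two correlated outcomes and specifies nothing that estimates or tests that difference. The chance of a false confirmation therefore depends on a rule not yet chosen: about 50% by the larger estimate and about 3% to 17% by one-significant-one-not, against 2.5% for a two-sided 5% test of the difference. These figures rest on assumed sample sizes, correlations and effect sizes, and on equal true effects.

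A reader might further infer that a significant difference would show the PHQ-9 to be more literacy-sensitive. The documents do not allow that step unaided. The SAP's section on sleep as a mediator between depression and pain notes that the PHQ-9 includes sleep questions and the PROMIS depression scale does not, and sleep disturbance is a predictor here. Some of a difference could come from that overlap.

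**What to change.** 1. Use one complete-case set for both outcomes, and standardize both.
2. Define the effect in advance as one summary. For example, take the mean of the five standardized Health LiTT-by-symptom interactions with each sign aligned to its prediction: S = (b_rumination − b_pain intensity − b_pain interference − b_sleep − b_fatigue)/5. Without this alignment, a difference pooled over symptoms has no defined direction, because the SAP predicts opposite signs for rumination and the somatic symptoms.
3. Report S for the PHQ-9 minus S for PROMIS with a 95% interval, from a bootstrap that resamples participants and refits both lm() models, or from a joint model. Give the per-symptom differences as description.
4. Call the prediction supported only if the interval lies above zero.
5. Add a sensitivity analysis with the PHQ-9 scored without its sleep content.
6. Label the contrast post hoc if these models have already been run. The version notes under Cognitive Correlates of Rumination say that some have, and the SAP's introduction requires analyses that were not pre-registered to be labelled in this way.

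No new data are needed. The cost is a short bootstrap loop, a paragraph of SAP text, and a wider interval with a more cautious conclusion.

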Using a large sample, we will determine the psychometric properties of health questionnaires across levels of health literacy. Testing will be conducted in English and Spanish, across two modes of administration (paper-and-pencil vs. talking touchscreen). Each participant will have three visits (baseline, 3-month, and 6-month follow-up), described below, in order to determine changes in psychometric properties over time. We will use *differential item functioning* (DIF) and other psychometric analyses to identify questionnaire items with varying characteristics across levels of health literacy. Before the COVID-19 pandemic, our original plan was to recruit $N = 1216$ participants for in-person assessments. At the time of this plan our final N is 728 participants who have completed a health literacy assessment; some of these participants are missing data on subsequent questionnaires. In-person recruitment was put on hold during the COVID-19 pandemic; in order to adapt the the pandemic, a subset of participants ($N = 304$) was invited to a phone-based protocol that included data collection about the impact of COVID-19, vaccine confidence, and health-related quality-of-life (PROMIS-29 profile).

- **Develop alternative modes of test administration that can better accommodate people with low health literacy.** National statistics indicate that 14% of adults in the United States have below basic reading skills, and over 75 million Americans have below basic or basic health literacy skills.¹⁴ These data strongly indicate that many individuals seeking health care will have difficulties with written questionnaires, even those that have been carefully developed such as those in the NIH PROMIS. We will test an alternative mode of administration that has been specifically designed to aid people of low health literacy – a computer-assisted “talking” version that uses speech technology that participants can privately access as needed to have items and response options

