read to them. We will analyze the talking touchscreen groups and paper-based groups separately. We hypothesize that the talking touchscreen will reduce health literacy-related test bias by level of health literacy, relative to traditional paper-based methods. This will be evidenced by fewer items being flagged for DIF in the group that receives the talking touchscreen. In terms of descriptive statistics to display the magnitude of effects, we will report effect sizes (McFadden's R^2) of DIF items, as well as test characteristic curves (TCCs) for DIF items. Among participants with low health literacy, we expect that the discrimination parameters of the touchscreen condition will be higher than the paper-based condition.

- **Determine the degree of differential item functioning (DIF) of tools relevant to clinical research across different levels of health literacy.** DIF analyses will be conducted to identify test bias by level of health literacy. This will ensure that individuals with low literacy are assessed fairly in clinical and research settings. We will assess a broadly applicable instrument to primary care – the PROMIS Profile, which measures anxiety, depression, fatigue, pain interference, pain intensity, physical function, sleep disturbance, and social roles and activities. Other questionnaires included in the study are shown in Table 1. We will stratify participants into low versus adequate literacy levels using Health LiTT (groups will be formed according to T scores of < 55 vs. 55+).¹⁵ A secondary analysis will use the NUMI, a measure of health numeracy, in three groups (low = 0-3, medium = 4-6, high = 7 or greater). Then, we will determine whether psychometric properties of each questionnaire scale are consistent for individuals with low health literacy versus adequate health literacy. We hypothesize that DIF will be observed for multiple scales using paper-and-pencil administration, suggesting a need to improve test items, and a need to examine alternative ways to administer these tools.

Statistical methodology

Overview

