We will determine the degree to which health literacy moderates the relationship between depression and associated constructs of rumination, pain intensity, pain interference, sleep disturbance, and fatigue. Depression will be measured using both the Patient Health Questionnaire (PHQ-9), a nine-item scale with each item scored between 0 and 3 providing a 0-27 severity score with higher scores representing greater depression severity. The NIH Patient-Reported Outcomes Measurement Information System (PROMIS Profile 57 v 2.0) will also be used to measure depression, as well as pain intensity, pain interference, sleep disturbance, and fatigue. PROMIS is a self-report measure with subscales producing a T-Score; higher T-scores representing a higher level of the construct. Rumination will be measured using the Ruminative Responses Scale (RRS) short form, a 10-item form that measures two factors, brooding and reflection. The RRS uses a four-point scale for each item with a total score derived from the sum of the individual items. Higher scores indicate higher levels of rumination. All variables will be examined in a continuous manner, rather than using cut scores.

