Mean centering. Because we plan to test interaction effects (i.e., moderation), we will mean-center brooding, reflection, PROMIS depression, age, and Health LITT. If any additional continuous covariates are used in exploratory analyses, these will also be centered around the mean.

Exploratory Structural Equation Modelling

All items in the cognition measures (as latent variables) and brooding and reflection (as scores) will be included (see above). Based on the parallel analysis to determine the number of factors, multiple exploratory factors from

the cognitive measures will be regressed on our two covariates of interest – brooding and reflection. We anticipate that brooding and reflection will be inversely related with cognition, in particular items related to memory and executive function. In other words, higher levels of rumination will be associated with lower levels of cognition.

We will conduct these analyses using Mplus. We will report all fit indices, unstandardized associations among variables, corresponding SEs, and significance tests at a Type I error rate of .05.

Scoring rumination

Rumination will be measured using the Ruminative Responses Scale (RRS) short form, a 10-item form that includes two subscales, brooding and reflection. The RRS uses a four-point response scale for each item with a total score derived from the sum of the individual items. Higher scores indicate higher levels of rumination. All variables will be examined in a continuous manner, rather than using cut scores. If 80% or more of the items are present, we will score the subscale using prorating.

Hypotheses and testable predictions

We hypothesize that rumination will have a significant association with cognition. Specifically, higher scores in both domains of rumination (brooding and reflection) will be related to lower scores on cognitive factors. Overall, we expect cognition to be more strongly related to brooding than reflection. In past work ([name] & Raes, 2014), we found that the brooding factor was more robust than the reflection factor. Thus, it is possible that the more reliable brooding scale will have larger associations with cognition. However, the literature contains mixed findings with regard to the relative contributions of brooding versus reflection (e.g.,^{57, 58}).

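### The variance-gain criterion in the depression moderation analysis can be met by a literacy main effect alone, and the symptom betas to be compared do not measure moderation

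*SAP*

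**What the plan says.** The SAP section *Prediction of depression: Health literacy as a moderator of rumination, pain, fatigue, and sleep disturbance* fits linear regressions with lm(), separately for PHQ-9 and PROMIS depression, "with health literacy (a continuous score from Health LiTT) acting as the proposed moderator". Symptom scores are entered together and health literacy is then added as a moderator. What the hypotheses lead the authors to expect is that "the addition of health literacy into the model should explain a significantly greater portion of the variance than symptom scores alone". PROMIS scales are then removed step by step to show what each contributes. The section next predicts a significant interaction with a direction: a stronger rumination link at higher literacy, and stronger somatic links at lower literacy. It closes the comparison of predictors with "We will also compare standardized beta coefficients to determine the strength of the effect for each variable".

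The section gives no model equation, no N and no centring rule. It does not say whether products enter together with Health LiTT, which test decides the interaction hypothesis, or which betas are compared. The general rule is "All hypothesis testing will be carried out at a two-tailed Type I error rate of $\alpha = .05$ unless otherwise specified". Centring appears only in the later plan, *Cognitive Correlates of Rumination*: "Because we plan to test interaction effects (i.e., moderation), we will mean-center brooding, reflection, PROMIS depression, age, and Health LITT". That plan also provides for simple slopes.

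**The concern.** Moderation means that the symptom slopes change with literacy. In the regression that information sits only in the symptom-by-Health LiTT products. The variance criterion takes symptoms alone as its comparator, so whatever Health LiTT predicts by itself counts towards the gain. A main effect is plausible: the SAP's later section on stress and trauma symptoms says that health literacy can be linked to conditions such as depression. A report could therefore describe a significant gain as in line with the moderation hypotheses when no slope differs by literacy.

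The second issue is the betas. Once products are in the model, the coefficient of a symptom is its slope at the point where Health LiTT equals zero. If zero is the sample mean, the beta describes a typical participant but says nothing about moderation. If zero is the raw origin of a T score, it describes nobody in the sample. Two analysts following the same text could rank the symptoms differently from the same data.

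**Working it through.** The section states no power, effect size or R-squared, so there is no planned figure to reproduce.

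**Inputs**
- Two-sided alpha .05 (SAP, Statistical methodology, Overview).
- N: "At the time of this plan our final N is 728 participants who have completed a health literacy assessment". This is an upper bound, because the SAP says some of them lack later questionnaires and this section uses listwise deletion. N = 304, a size used elsewhere in the SAP, serves only as a lower illustration.
- Five symptom predictors, counted from the section's list: rumination, pain intensity, pain interference, sleep disturbance, fatigue.
- Assumed: literacy partial r of .10 or .15 given symptoms, and no interaction.

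**Variance criterion.** The noncentrality is N × r²/(1 − r²). For N = 728 it is 728 × .01/.99 = 7.35 and 728 × .0225/.9775 = 16.76. For N = 304 it is 3.07 and 7.00. Rejection probabilities from the noncentral F:

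| N | Step added to symptoms | df | r = .10 | r = .15 |
|---|---|---|---|---|
| 728 | Health LiTT + 5 products | 6, 716 | 49% | 88% |
| 728 | Health LiTT alone | 1, 721 | 77% | 98% |
| 304 | Health LiTT + 5 products | 6, 292 | 21% | 46% |
| 304 | Health LiTT alone | 1, 297 | 42% | 75% |

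All of these are significant gains without moderation.

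**Products-only step.** I simulated 1,500 data sets per setting. Assumptions: symptom intercorrelation .4 (.7 between the pain scales), symptom–literacy correlation −.15, residual variance .55. The 5-df test of the products over symptoms plus Health LiTT rejects in .047–.059 (N = 728) and .044–.064 (N = 304) of data sets when there is no moderation, for literacy main effects from 0 to −.20. With moderation only (+.10 rumination, −.10 fatigue, no main effect, N = 728) its power is about .88, against .05 for adding Health LiTT alone. So on that reading the variance criterion would also miss real moderation.

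If the interaction hypothesis were judged by any one of five uncorrected products, the false-positive rate would be 1 − .95⁵ = .226 under independence, and .19–.23 in the simulation.

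**Betas.** The SAP treats Health LiTT as a T score ("groups will be formed according to T scores of < 55 vs. 55" and above), and "PROMIS is a self-report measure with subscales producing a T-Score". Mean 50 and SD 10 are assumed. Zero is then (50 − 0)/10 = 5 SDs below the mean, so the slope at Health LiTT = 0 is the slope at the mean minus 5 × the interaction. With an interaction in the hypothesised direction (+.05 rumination, −.025 each somatic scale):

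| Scale | Slope at mean literacy | Slope at Health LiTT = 0 | Simulated beta, raw products |
|---|---|---|---|
| Rumination | .35 | .35 − .25 = .10 | .09 |
| Fatigue | .20 | .20 + .125 = .325 | .33 |
| Sleep disturbance | .15 | .275 | .27 |
| Pain interference | .10 | .225 | .22 |
| Pain intensity | .05 | .175 | .20 |

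Rumination moves from first to last. With a smaller interaction (+.03, −.015) raw products give rumination .19 and third place. At N = 728 the top-ranked symptom differs between raw and centred coding in 94% of data sets at +.05/−.025. It still differs in 48% with no interaction, because the standard error of a symptom slope at zero is about √(1 + 5²) = 5.1 times that at the mean.

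With centred variables the betas stay at about .35, .20, .15, .10 and .05 whether the rumination interaction is .03 or .10. Even correctly coded, they rank slopes at mean literacy and carry no information on moderation.

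**The case against.** The strongest reply is that the section does not rest on the variance gain alone. It expressly predicts a significant interaction with a direction, and a pure main effect would not satisfy that. The test of a product term also does not depend on centring. This stands. A reader might infer that moderation could be declared from a main effect alone; the documents do not support that, because the main effect meets one stated expectation and not the other. What remains is that the interaction hypothesis has no named test, while the variance expectation has an explicit comparator, and it is the wrong one for moderation.

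A second reply is that the added step may be an ordinary main-effect step, with the interaction tested afterwards. The text allows this. But the section describes the step as adding literacy as a moderator and presents the gain as in accord with its hypotheses, and on this reading the gain contains no moderation at all.

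A third reply is that the SAP never says raw products will be used. If variables are z-scored before products are formed, centring is automatic and the ranking problem disappears. This also stands. A reader might infer that the betas will be read at Health LiTT = 0, or that they decide which scales the step-down removes. The section says neither. Nor is the symptom ranking one of its hypotheses; the comparison of betas is a single descriptive sentence.

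**Conclusion.** The concern holds in a limited form. The stated variance criterion does not isolate moderation on either reading of the added step. With no moderation it is met in 21% to 98% of cases over the assumed range (N of 304 or 728, partial r of .10 or .15). The separate interaction prediction limits the damage but does not supply a test. That much does not depend on the assumed values; only the percentages do.

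Standardized symptom betas from a model with products do not measure moderation under any coding. The change in ranking is conditional: it requires raw-score products, which this section does not exclude, and its size depends on the interaction and on the assumed mean 50 and SD 10 for Health LiTT.

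**What to change.** Write out the model in this section, for each outcome:
1. Centre or standardize the symptom scores and Health LiTT before forming products.
2. Fit symptoms; add Health LiTT; then add all symptom-by-Health LiTT products.
3. Name the F test of the products-only step as the moderation criterion. Report the Health LiTT step as a main effect.
4. Report each interaction coefficient with its confidence interval, and the symptom slopes at mean literacy and at plus and minus 1 SD. State how individual products are judged across five scales and two outcomes.
5. In the step-down, remove a scale together with its product.

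This takes SAP wording and a few lines of R, with no new data. One cost should be stated openly. The version notes to *Cognitive Correlates of Rumination* (Version 4.2, June 2021) say that some analyses under this section had already been carried out. For those results the change may need to be documented with justification, as the SAP's Overview requires, or labelled post hoc.
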